Test Article(s)	
 
• Video: ~15-minute interactive video focused on education related to acute pain management strategies
 
• Telecare: ~15-minute follow-up phone call by a nurse occurring 48-72 hours after the ED visit to assess patient's pain management strategies and provide recommendations
 
• Primary Care Provide (PCP) Communication: summary of patient's ED visit and telecare call will be provided to patient's PCP
 

Study Design	This is a three-arm, parallel group, randomized controlled trial.
Subject Population	Inclusion Criteria
Key Criteria for Inclusion and Exclusion:	
1. ED patients age 50 and older
 
2. Primary complaint of acute musculoskeletal pain
 
3. If in the ED, expected discharge
 
Exclusion Criteria
 
1. Pain located in the head, chest, or abdomen or due to ischemia, infection
 
2. Patients who are critically ill
 
3. Self-reported daily opioid use for more than 2 weeks prior to the acute care visit

Number of Subjects	400
Study Duration	
Each subject's participation will last 12 months.
 
The entire study is expected to last 5 years.

Study Phases	
 
1. Screening: screening for eligibility, obtaining consent and HIPPA agreement will occur over the phone at the time of enrollment
 

Screening	
Study Treatment	
 
2. Baseline: data collection will occur for subjects in all arms of the study over the phone within 24 hours of their ED or OrthoNow visit
 

Follow-Up	
 
3. Randomization: subjects will be randomly assigned to 1 of 3 study arms at enrollment
 
4. Intervention: 
 
a. an educational video shown to subjects in the full and video-only intervention arms of the study
 
b. telecare phone call ~48 -72 hours after study enrollment for subjects in the full intervention group
 
c. PCP communication for subjects in the full intervention group
 
 
 
5. Follow up: data collection will occur via phone interview for subjects in all arms of the study at 1 week, 1, 3, 6, and 12 months
 

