## 1.2 Name and Description of Intervention

The intervention entails an educational video, Brief Educational Tool to Enhance Recovery (BETTER from Pain), in addition to telecare and primary care provider (PCP) communication.

**BETTER from Pain Video:** A ~15-minute interactive educational video sent to patients via email or text after study baseline questions are completed. Patients watch the video within 24 hours of their acute care visit. The video provides information about acute pain management strategies that can be used at home including medications (acetaminophen, NSAIDs, opioids) and behaviors (sleep, staying active, relaxation, and social support).

**Telecare:** A ~15-minute protocol-guided phone call from a research nurse ~48-72 hours after the patient's enrollment in the study. Telecare is designed to assess the patient's pain severity and interference with daily activities, review analgesic and opioid use and side effects, review recovery-promoting behaviors discussed in the video (sleep, staying active, relaxation, and social support), discuss adjustments to the patient's treatment, and link the patient to PCP follow-up.

**PCP Communication:** The research nurse will provide a summary of the ED/OrthoNow visit and telecare call to the patient's primary care provider (PCP) in order to convey information about the patient's condition and treatment plan with the intent of supporting a transition of care. Patients without a PCP provider will be provided resources for one.

This study entails two intervention groups: **Full intervention** and **video-only intervention**. The Full intervention group will receive all three components of the intervention (video + telecare + PCP communication) while the video-only group will only receive the video.

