## 9 SAFETY MANAGEMENT

### 9.1 Adverse Event Reporting

All adverse events (AEs) and serious adverse events (SAEs) that are spontaneously reported to study personnel (SC, RN, RAs, or investigators) or elicited by them during subject interviews or contacts will be promptly reported to the PI and RN. The PI or RN will determine if AEs and SAEs are related or unrelated to the research intervention and if they are expected or unexpected occurrences. AEs will be reported to the PI or RN within 24-48 hours of the event; SAEs will be reported to the PI or RN as soon as the event is known. AE/SAE information will be recorded in REDCap. The RN will maintain a tracking log of AEs and SAEs which will be reviewed by the PI on a monthly basis. The tracking log will also be summarized and reported to the IRB annually and to the SO and NIA twice yearly in biannual reports. Serious Adverse events will be reported by the PI or RN to the SO, IRB and NIA within 24 hours of notification.

An AE is any untoward physical or psychological occurrence in a human subject participating in research. An AE can be any unfavorable or unintended event. For this trial the most common AE's will include:

- Side effects related to analgesic medications being recommended as part of the study
- Emergency department visits
- Other events about which study personnel are uncertain should be reported to the PI or RN who will discuss and decide if it qualifies as a reportable AE

AEs will be classified according to severity, which is based on their impact on the patient. An AE will be termed "mild" if it does not have a major impact on the patient, "moderate" if it causes the patient some minor inconvenience, and "severe" if it causes a substantial disruption to the patient's well-being. All AEs will be documented in REDCap.

AEs requiring prompt reporting will include the following 3 criteria:

- Unexpected (in terms of nature, severity, or frequency) given (a) the research procedures that are described in the protocol-related documents, such as the IRB-approved research protocol and informed consent document and (b) the characteristics of the subject population being studied

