Reducing the Transition from Acute to Chronic Musculoskeletal Pain among Older Adults

(BETTER from Pain)

NCT number NCT04118595

Document Date 07/24/2022

**Reducing the Transition from Acute to Chronic
Musculoskeletal Pain among Older Adults**

(BETTER from Pain Study)

Statistical Analysis Plan

Version 1.1

This statistical analysis plan is an expanded version of the summary analysis plan included in the study protocol and supersedes the summary plan included in the study protocol. Any significant changes made to this analysis plan after study initiation will be documented herein.

1. Study Objectives

The objectives of this 3-arm randomized trial are as follows:

Objective 1: To evaluate the effects of two Shared Decision Making based interventions (full and video-only intervention) relative to Usual Care on musculoskeletal pain (MSP), as measured by the combined pain severity and interference scores from the Brief Pain Inventory Short Form (BPI-SF), through 6 months following the initial visit.

Sub-Objective 1a: To evaluate the intervention effects separately on the two components of the BPI-SF, pain severity and interference, evaluating both longitudinal change through 12 months and differences at discrete time points of 1, 3, 6, and 12 months.

Sub-Objective 1b: To evaluate the intervention effects over time on other key secondary outcomes, including opioid use, analgesic-related side effect frequency and severity, physical function, overall health, sleep quality, and healthcare utilization.

Objective 2: To assess the mechanisms by which the interventions (full and video-only) influence outcomes.

Objective 3: To estimate the incremental cost per case of persistent pain (defined as pain ≥ 4 on 0-10 scale present at one year) prevented by either the full or video-only intervention compared with usual care.

This document describes the analyses planned for Objectives 1 and 2, and other supporting quantitative analyses. The cost-effectiveness analysis to be applied for Objective 3 will be described elsewhere.

2. Study Design Overview

Four hundred patients presenting with acute MSP recruited from four sites (3 emergency departments (EDs) and one Urgent Care) will be randomized to one of three arms:

1. **Full Intervention** (video + telecare + primary care provided (PCP) communication)
2. **Video-only Intervention** (video but no telecare or PCP communication)
3. **Usual Care**

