To address the Objective 2, we will apply structural equation models (specifically, longitudinal path analyses with manifest variables) with all variables incorporated appropriately for their scale. The structural equation models will be fit using MPlus software, version 8.3 or higher. The models will use data from all participants and will control for the same baseline variables as for the primary objective. Full maximum likelihood methods will be used, which allow for inclusion of all observed data for participants who contribute incomplete data. The primary model will include direct and indirect effects from the interventions to the longitudinal outcomes through potential mediating variables (self-efficacy and other “process-related” variables measured at the 1-week phone call) to allow for assessment of whether mediation is present, and if so, whether it is complete or partial. No structural relationships will be imposed relating the potential mediating variables to one another, beyond simple correlations. For the longitudinal outcomes, we will include Pain Severity and Interference in the model as separate variables, which we will allow to be correlated at each time point. We will first test each of the path coefficients from the interventions to the mediator variables separately at the $p=0.05$ level using chi-squared difference tests. We will then test indirect paths to assess mediation. We will compare full and reduced models (with selected paths restricted to be zero) using chi-squared difference tests. Standard model fit indices (i.e., RMSEA, Bollen’s incremental index, and the Tucker-Lewis index) will be reported.

A schematic diagram of the general model set up is shown in Figure 1 below. In this figure, straight arrows represent structural paths, curved arrows represent correlations.

12. Summary of Safety Data

Adverse events will be descriptively summarized for the ITT Population, by randomized treatment group, using frequency tables. Summaries will also be presented according to severity and perceived relatedness to the study. No inferential statistics (hypothesis tests or confidence intervals) will be presented for comparing across groups.

Figure 1. Schematic diagram of the proposed longitudinal path model.

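### SAP 12 compares adverse event counts by arm although only the full arm has an extra nurse call about side effects, so its counts are liable to be inflated by ascertainment

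*SAP*

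**What the plan says.** SAP section 12 sets out the safety analysis: "Adverse events will be descriptively summarized for the ITT Population, by randomized treatment group, using frequency tables". It adds breakdowns by severity and perceived relatedness, and then says: "No inferential statistics (hypothesis tests or confidence intervals) will be presented for comparing across groups".

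The Protocol synopsis reserves one contact for a single arm: "telecare phone call ~48 -72 hours after study enrollment for subjects in the full intervention group". SAP section 2 describes the video-only arm as "video but no telecare or PCP communication". Protocol 1.2 lists among the purposes of the telecare call to "review analgesic and opioid use and side effects".

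Protocol 9.1 covers all events "spontaneously reported to study personnel (SC, RN, RAs, or investigators) or elicited by them during subject interviews or contacts". The research nurse is among the staff named. The first of the adverse events expected to be most common is "Side effects related to analgesic medications being recommended as part of the study". Under Protocol 9.2, depressive symptoms voiced at telecare or at a telephone interview lead to a suicide assessment, and every such assessment is recorded as an adverse event.

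All arms share five follow-up calls, at 1 week and at 1, 3, 6 and 12 months (Protocol 3.1), and the side-effect scale is asked at each of them (Protocol 5.3).

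**The concern.** A by-arm table of adverse events is read as a comparison of arms. That is fair only if each arm had a similar chance of having events found. Here one arm has an additional conversation with a nurse, and its topic is the leading category of expected adverse events. A side effect mentioned then and not mentioned again at a later call is counted in the full arm and lost in the other two. The suicide assessment route likewise has one more opportunity in the full arm.

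Neither the SAP nor the protocol records the contact at which an event was reported, restricts the table to shared contacts, or warns of unequal ascertainment. What is at stake is interpretation: the full intervention could appear to carry more adverse events than video-only or usual care for a reason unrelated to safety. No efficacy analysis is touched.

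**Working it through.** The plan gives no adverse event rate, so there is no stated figure to reproduce.

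**Step 1: count the contacts.** Full arm: 1 telecare call + 5 common calls = 6. Video-only and usual care: 5 each. 6/5 = 1.20. For participants not admitted to hospital, telecare may run to day 7 and the 1-week call falls on days 7 to 12 (Protocol, table of data collection periods). By day 12 the count is therefore two contacts versus one. These are opportunities to report, not an estimate of excess events.

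**Step 2: illustrate the size under equal true risk.** About 133 patients per arm comes from Protocol 3.3. The other three inputs are assumptions:
- π = true risk of at least one adverse event, 0.2 to 0.6
- s = chance that the common calls record it, 0.5 to 0.9
- e = chance that telecare records an event the common calls miss, 0 to 0.5

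Recorded risk in the other arms = π × s.
Recorded risk in the full arm = π × (s + (1 − s) × e).
Ratio = 1 + (1 − s) × e / s, which does not depend on π.

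| Case | Other arms, of 133 | Full arm, of 133 | Ratio |
|---|---|---|---|
| e = 0, any s (shown: π 0.4, s 0.7) | 37.2 | 37.2 | 1.00 |
| π 0.4, s 0.9, e 0.5 | 47.9 | 50.5 | 1.06 |
| π 0.4, s 0.7, e 0.3 | 133 × 0.28 = 37.2 | 133 × 0.316 = 42.0 | 1.13 |
| π 0.6, s 0.5, e 0.5 | 133 × 0.30 = 39.9 | 133 × 0.45 = 59.8 | 1.50 |

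The artificial excess runs from 0 to about 20 patients. It is small when the common calls capture most events.

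**Step 3: check two possible corrections in the middle case.**
- *Count only events first reported at a common contact.* Telecare comes before the 1-week call, so an event voiced at both leaves the table in the full arm but stays in the others. Suppose that all events begin before telecare and that telecare also hears 30% of those the common calls would record. The full arm then shows 133 × 0.28 × 0.70 = 26.1 against 37.2, a ratio of 0.70. That error is larger than the one being corrected, and in the opposite direction.
- *Count events captured at a common contact, whether or not telecare heard them first.* Both arms show 133 × 0.28 = 37.2, a ratio of 1.00.

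**The case against.** The best defence is that the fair comparison is already planned. SAP Sub-Objective 1b makes side-effect frequency and severity a key secondary outcome. SAP 5d defines the modified OR-SDS, and SAP 10 compares it between arms. It is asked on one schedule in all arms, by interviewers described as blinded. The adverse event table, by contrast, is descriptive. This stands, and it limits the harm. It does not make the table in section 12 comparable across arms, and section 12 does not point the reader to the OR-SDS result.

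The 1-week call puts the side-effect scale to everyone within days of telecare, so much of what telecare hears would be reported again. This also stands, and it is why the ratio may be close to 1.00. Emergency visits and hospitalizations are abstracted from the health record in all arms (Protocol 4.5 and 5.1), so they depend much less on an extra call.

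The Protocol synopsis refers to a separate Data and Safety Monitoring Plan for how adverse events are recorded. Source or de-duplication rules may be there. That plan is not among the documents reviewed, and section 12 does not use any such rule.

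A reader might go further and infer that the full arm will look less safe, or that its counts are raised by 20%. The documents support neither. The 20% is a ratio of contacts and would measure inflation only if each contact yielded new, unrelated events. The intervention may also truly reduce side effects, so the observed difference could go either way. Nor do the documents say when side effects are most frequent.

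**Conclusion.** The point holds as a limit on interpreting one descriptive table. The direction of the ascertainment difference is known: it raises full-arm counts relative to both other arms. Its size is not known. The range of 1.00 to 1.50, and the middle case of 42 versus 37 patients, rest on assumed detection values, equal true risk, and telecare leaving later reporting unchanged. No test, confidence interval or error rate is affected, because section 12 plans none. This is a minor improvement to the plan, worth making because it costs little.

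**What to change.** 1. Record every contact or source at which each adverse event was reported, not only the first. Staff on the common calls should log an event even if telecare has already reported it.
2. Keep the table of all events by arm.
3. Add a by-arm table of events captured at the 1-week, 1-, 3-, 6- or 12-month calls or in the health record, including those also mentioned at telecare. Health record here should mean the follow-up abstraction done in all arms. It should not include the note that the nurse writes into the record after telecare (Protocol 4.4), which would bring the asymmetry back.
4. List events captured only at telecare separately, so that none is lost.
5. State in SAP 12 that the all-events table has unequal ascertainment and that the planned OR-SDS analysis is the like-for-like comparison of side effects.

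Do not restrict the table to events first reported at a common contact, for the reason shown in the working.

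The cost is one source field and one extra table. For events already recorded, the separate telecare instrument in REDCap (Protocol 4.4) should help to identify the source.
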